4.0 OVERVIEW OF STUDY DESIGN/INTERVENTION

4.1 Design

A single-center, single-arm, open-label phase II study evaluating the combination of tafasitamab and lenalidomide for treatment of adults with R/R MCL who have previously failed or could not tolerate BTKi therapy. Patients will be eligible if they have received one or more prior lines of therapy, one of which must have been a BTKi. Patients will be enrolled according to a Simon two-stage design, described in 14.0, with early stop criteria for lack of efficacy.

Tafasitamab will be administered intravenously and lenalidomide will be self-administered orally according to the treatment schema in 4.2. The primary endpoint is ORR (CR plus PR)

[figure not shown]

evaluated by PET/CT according to Lugano criteria at the end of cycle 12 or treatment discontinuation, whichever is earlier.^{1,2}

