2.0 OBJECTIVES AND SCIENTIFIC AIMS

2.1 Primary objective

The primary objective of this study is to assess the ORR, defined as the percent of patients (relative to the total number considered evaluable as in 13.2) who achieve complete response (CR) or partial response (PR) according to the 2014 Lugano response criteria for non-Hodgkin lymphoma (NHL), to the combination of tafasitamab and lenalidomide in patients with R/R MCL who have experienced failure of or intolerance to past treatment with BTKi.^{1,2}

Figure 1: Treatment schema

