2.2 Secondary objectives

- 2.2.1** To determine disease control rate (DCR), defined as the percent of patients (relative to the total number evaluable) who achieve CR, PR, or stable disease (SD) at the time of ORR assessment.
- 2.2.2** To estimate DOR, defined as the time from achievement of PR or CR to progression of disease (POD) according to Lugano criteria.^{1,2}
- 2.2.3** To estimate PFS, defined as the time from initiation of study treatment to the earlier of POD or death from any cause.
- 2.2.4** To estimate OS, defined as the time from initiation of study treatment to death from any cause.
- 2.2.5** To estimate TTP, defined as the time from initiation of study treatment to POD or death from MCL.
- 2.2.6** To describe the safety of the combination of tafasitamab and lenalidomide in patients with R/R MCL, defined as the incidence and severity (according to National Cancer Institute Common Terminology Criteria for Adverse Events (CTCAE) version 5.0).

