After BTKis were established as a standard second-line treatment option for R/R MCL, there was interest in defining outcomes associated with lenalidomide-based therapy after BTKi failure or intolerance. This was evaluated in the retrospective MCL-004 study of a cohort of 58 patients with R/R MCL (13 treated with lenalidomide monotherapy, 11 with lenalidomide and rituximab, and 34 with other lenalidomide combinations).²² Patients had received median four prior lines of therapy (range 1-13), with an ORR of 29% (14% CR) and median duration of treatment of 8.4 weeks. The median DOR for responders was 20 weeks.

Tafasitamab in B-ce/1 NHL

Tafasitamab (MOR00208, previously XmAb5574) is an Fe-engineered, humanized monoclonal antibody that binds to the human B-cell surface antigen CD19.²³ CD19 is broadly expressed across the B-lymphocyte lineage, including in B-cell malignancies, but not by hematological stem cells. Tafasitamab produces significantly higher tumor cytotoxicity compared to the parental, non-engineered, murine 4G7 CD19 antibody. Tafasitamab has increased affinity for Fey receptors through the introduction of two amino acid modifications within the Fe region. Tafasitamab is associated with antibody-dependent cellular cytotoxicity (ADCC), antibody-dependent cellular phagocytosis, and exerts direct cytotoxicity. Preclinical studies indicate potent in vitro and in vivo activity of tafasitamab in lymphoma and leukemia models.^{23,24}

Tafasitamab was tested in a phase IIa study in B-cell NHL, including diffuse large B-cell lymphoma (DLBCL), follicular lymphoma (FL), other indolent NHL, and MCL.²⁵ Patients received tafasitamab 12mg/kg IV once weekly for 8 weeks, with those achieving at least SD eligible to continue treatment for an additional 4 weeks. Patients who achieved PR or CR after 12 weeks could receive further extended treatment every 2 or 4 weeks until POD. The primary endpoint of this study was ORR. Ninety-two patients were enrolled: 35 patients with DLBCL, 34 with FL, 11 with other indolent NHL, and 12 with MCL. Responses were observed among patients with DLBCL, FL, and other indolent NHL (ORR 26%, 29%, and 27%, respectively), including several durable responses. Among patients with MCL, there were no responders; however, six patients (50%) achieved SD, while five (42%) progressed and one

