4.2 Intervention

Patients will receive treatment with intravenous tafasitamab and oral lenalidomide for up to 12 cycles. Each cycle is 28 days in length. Lenalidomide will be self-administered at a dose of 20mg daily days 1-21 of cycles 1 through 12. During the first cycle, tafasitamab will be administered on days 1, 4, 8, 15, and 22. During cycles 2 and 3, tafasitamab will be administered weekly on days 1, 8, 15, and 22. During cycles 4 through 12, tafasitamab will be administered every other week on days 1 and 15. Upon earliest of completion of cycle 12 or EOT, patients will undergo radiologic evaluation of response. Patients who achieve SD, PR, or CR at completion of cycle 12 will continue tafasitamab maintenance therapy on day 1 of each cycle until the earliest of POD or 36 cycles (inclusive of the first 12 cycles).

Figure 1: Treatment schema

*One cycle = 28 days

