14.0 BIOSTATISTICS

Objectives:

The primary objective is to estimate the ORR, defined as the percent of patients (relative to the total number considered evaluable as in 13.2) who achieve CR or PR. The primary endpoint will be analysed when all patients have completed 12 cycles of treatment or at treatment discontinuation, whichever comes first.

Secondary objectives are estimates of OCR, DOR, PFS, OS, and TTP, and descriptions of incidence and severity of AEs. Exploratory objectives include rate of conversion to undetectable MRD, ctDNA/clonal evolution, antitumor immune response, and effects on tumor microenvironment immunosuppression.

Exploratory objectives are described in Section 3.1 Correlative studies.

Study design:

The primary endpoint is ORR and the study is designed to determine preliminary clinical effectiveness of tafasitamab and lenalidomide. Based upon limited data available for lenalidomide and associated combinations in the post-BTKi setting, the combination of tafasitamab and lenalidomide will be considered worthy of further evaluation if the ORR is greater than 30%. This combination will be considered promising in the R/R setting if the ORR is greater than 50% given multiple evolving treatment options for patients post-BTKi failure or intolerance. To this end, , a single-arm Simon's two-stage minimax design will

utilize a null (non-promising) ORR of 30% and an alternative (promising) ORR of 50%. In the first stage, a total of 19 patients will accrue. If 6 or fewer have objective response, the trial will close due to a lack of efficacy; otherwise, an additional 20 patients will accrue. If at the end of the study, 17 or more out of 39 have an objective response, the trial will be considered promising for future development. This design will give 80% power with a type I error rate of 5%. Patients will continue to enroll without holding enrollment while the interim analysis is evaluated in the first 19 patients.

The anticipated accrual rate for this study is 1 to 2 patients per month. We anticipate total accrual will be completed in 2-3 years. The study will continue enrollment until the required number of evaluable patients (those that receive at least one dose of both study drugs) is reached in each stage of the study.

Methods:

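### The primary ORR is defined both as response status at cycle 12 or discontinuation and as response achieved, and the stated 80% power holds only for the second

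*Combined protocol and SAP*

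**What the plan says.** Three places point to a single reading of response:

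- Section 4.1 has the primary ORR "evaluated by PET/CT according to Lugano criteria at the end of cycle 12 or treatment discontinuation, whichever is earlier".
- Section 4.2 puts the scan at the same moment: "Upon earliest of completion of cycle 12 or EOT, patients will undergo radiologic evaluation of response".
- Section 2.2.1 defines disease control as CR, "PR, or stable disease (SD) at the time of ORR assessment", and Section 14.0 repeats this. The wording presumes one assessment time.

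Other places point to response achieved at any time:

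- Section 2.1 counts patients "who achieve complete response (CR) or partial response (PR) according to the 2014 Lugano response criteria", and Section 14.0 uses the same verb. Neither names a visit.
- Sections 1.0 and 14.0 mention 12 cycles or discontinuation only as the time when the endpoint is analysed.

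No section uses the term best response. Section 14.0 sets the design to "utilize a null (non-promising) ORR of 30% and an alternative (promising) ORR of 50"%, with a stop at 6 or fewer responses in 19 and a promising result at 17 or more in 39. It ties the 30% to limited post-BTKi data on lenalidomide and its combinations. The one such result in Section 3.0 is a retrospective cohort "with an ORR of 29% (14% CR) and median duration of treatment of 8.4 weeks", with a median response duration of 20 weeks. The 50% is justified by the evolving treatment options, without a cited rate.

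**The concern.** Take a patient in PR at an early scan who progresses in cycle 8 and stops treatment. Under Section 4.1 the reading is made at discontinuation, shows progression, and the patient is a failure. Under Section 2.1 the same patient achieved PR and is a responder. Two decisions depend on that count, and one patient can tip either: 6 versus 7 of 19, and 16 versus 17 of 39.

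The two definitions also sit on different scales. A null drawn from an any-time response rate does not fit a status reading at week 48. If the lower status rate is held against the 30%/50% thresholds, an active regimen can be closed at stage 1 or called not promising because some of its responses ended before cycle 12 was complete.

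**Working it through.** **Inputs from the documents.** Stage 1 has n = 19 and stops at 6 or fewer; the total is 39, promising at 17 or more; null 0.30, alternative 0.50 (Section 14.0). "Each cycle is 28 days in length" (Section 4.2), so 12 cycles are 12 × 28 = 336 days = 48 weeks. Median response duration is 20 weeks in the post-BTKi cohort and 16.3 months in the NHL-003 lenalidomide subset (Section 3.0). 16.3 months = 16.3 × 365.25 / 12 / 7 = 70.9 weeks.

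**Step 1: reproduce the plan's figures.** With b the binomial probability,

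P(promising | p) = Σ over x = 7 to 19 of b(19, x, p) × P(Bin(20, p) ≥ 17 − x).

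- p = 0.30: 0.0455 (stated 5%); stage 1 stop 0.666.
- p = 0.50: 0.804 (stated 80%); stage 1 stop 0.084.

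The design is correct for whichever response rate is actually counted.

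**Step 2: effect of a status reading.** Let s be the assumed share of any-time responders still in response at the reading. The ORR as read is then p × s.

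| s | ORR as read, any-time 50% | Power | Stage 1 stop | Type I error, any-time 30% |
|---|---|---|---|---|
| 1.00 | 0.500 | 0.804 | 0.084 | 0.0455 |
| 0.95 | 0.475 | 0.710 | 0.122 | 0.029 |
| 0.90 | 0.450 | 0.599 | 0.173 | 0.017 |
| 0.80 | 0.400 | 0.356 | 0.308 | 0.005 |
| 0.70 | 0.350 | 0.156 | 0.481 | 0.001 |

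This table assumes no shape for response duration.

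**Step 3: plausible values of s.** Assume exponential response duration with median m weeks, first response at week t, and a reading at week 48. Then s = 0.5^((48 − t)/m). The range t = 8 to 24 is an assumption. Any-time ORR is 50%.

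| m | t | s | ORR as read | Power | Stage 1 stop |
|---|---|---|---|---|---|
| 70.9 | 8 | 0.676 | 0.338 | 0.121 | 0.525 |
| 70.9 | 12 | 0.703 | 0.352 | 0.161 | 0.475 |
| 70.9 | 24 | 0.791 | 0.395 | 0.334 | 0.323 |
| 20 | 8 | 0.250 | 0.125 | < 0.001 | 0.994 |
| 20 | 12 | 0.287 | 0.144 | < 0.001 | 0.987 |
| 20 | 24 | 0.435 | 0.218 | 0.002 | 0.901 |

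The last power figure is 0.0017 before rounding.

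**Step 4: the scale of the 30% null.** Under the same assumptions with m = 20, an any-time rate of 29% would be read at week 48 as 0.29 × 0.25 = 7% to 0.29 × 0.435 = 13%. Run backwards, a week-48 status rate of 29% would need an any-time rate of 0.29 / 0.435 = 67% at t = 24, and an impossible 0.29 / 0.25 = 116% at t = 8. With median treatment of only 8.4 weeks, the 29% is best understood as response at any time.

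**The case against.** The strongest reply is that the protocol never adopts a landmark endpoint. The objective counts patients who achieve a response. The 12-cycle wording in Sections 1.0 and 14.0 concerns when to analyse. Section 14.0 makes non-responders only of patients who withdraw before response evaluation. Duration of response starts at achievement of PR or CR, and Section 13.1 has tumor assessments made periodically. This stands: a reader might infer that early progressors are settled non-responders, but the sections conflict and do not decide it. The conflict is itself the defect, because the section that states the endpoint in most detail is the one that fixes the reading.

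Three other stronger inferences do not hold:

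- **That both 30% and 50% come from any-time response rates.** Only the 30% is tied to data, and no section labels the 29% as best response; that is inferred from the treatment and response durations. The 50% is a judgement.
- **That duration of response is inflated by a guaranteed period of about nine months.** This would need responders to be selected at cycle 12 and timed from first response. No section restricts the analysis that way.
- **That power is close to zero.** That needs the 20-week median, which comes from a cohort the protocol hopes to improve on. Step 3 also treats every responder who stops early as having progressed. Section 4.1 alone would count a patient who stops while in response as a responder, which raises the figures. Section 13.2, which fails anyone removed for a reason other than progression, may reverse that.

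It is also fair that status at cycle 12 is a legitimate endpoint, provided the null and alternative are set on that scale.

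**Conclusion.** The point holds as an inconsistency in the primary endpoint, with a conditional loss of power. If "at the end of cycle 12 or treatment discontinuation, whichever is earlier" is applied literally and the true any-time ORR is 50%, the stated 80% power does not hold. It is 60% if 10% of responders have progressed by the reading and 36% if 20% have. With exponential duration and first response at week 8 to 24, power is 12% to 33% for a 16.3-month median (stage 1 stop 32% to 53%), and below 0.2% for a 20-week median.

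The error runs one way. Type I error on the any-time scale falls, so there is no added risk of falsely declaring promise; the risk is false stopping or a false negative conclusion. If ORR is counted as response achieved, nothing is lost. The size therefore depends on which section is followed and on assumed durations. The need to choose one definition depends on neither.

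**What to change.** In Sections 2.1, 4.1, 4.2, 13.2 and 14.0, define ORR as best response: CR or PR by Lugano at any assessment through the end-of-cycle-12 assessment, before progression or new anti-lymphoma therapy. Keep cycle 12 or discontinuation as the time of analysis. Use this one definition for the 6/19 and 17/39 counts, and settle it before the stage 1 count. In the same edit, reconcile Section 13.2 with Section 14.0 for a patient who responds and then leaves for a reason other than progression.

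On this definition N = 39, 80% power and 5% type I error stand. The change uses assessments already scheduled and needs protocol wording only, although it does fix how the primary endpoint is counted. The downside is that ORR no longer implies durability, which duration of response and PFS already cover.

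If status at cycle 12 or discontinuation is truly intended, say so in every section and restate the null, the alternative and the power on that scale.

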4.2 Intervention

Patients will receive treatment with intravenous tafasitamab and oral lenalidomide for up to 12 cycles. Each cycle is 28 days in length. Lenalidomide will be self-administered at a dose of 20mg daily days 1-21 of cycles 1 through 12. During the first cycle, tafasitamab will be administered on days 1, 4, 8, 15, and 22. During cycles 2 and 3, tafasitamab will be administered weekly on days 1, 8, 15, and 22. During cycles 4 through 12, tafasitamab will be administered every other week on days 1 and 15. Upon earliest of completion of cycle 12 or EOT, patients will undergo radiologic evaluation of response. Patients who achieve SD, PR, or CR at completion of cycle 12 will continue tafasitamab maintenance therapy on day 1 of each cycle until the earliest of POD or 36 cycles (inclusive of the first 12 cycles).

Figure 1: Treatment schema

*One cycle = 28 days

5.0 THERAPEUTIC/DIAGNOSTIC AGENTS & NON-THERAPEUTIC ASSESSMENTS

5.1 Tafasitamab

Tafasitamab, also known as MOR00208, is an intravenously-administered CD19 monoclonal antibody manufactured by Morphosys. The Morphosys tafasitamab investigational new drug (IND) application will be cross-referenced by MSKCC.

Dose Formulation: Tafasitamab-cxix will be supplied as 200mg lyophilized powder in single-use vials by Morphosys

- Preparation:

- o Lyophilized powder should be reconstituted with 5ml sterile water for injection to a concentration of 40mg/ml
- o Sterile water for injection should be directed toward the vial wall, then gently swirled until powder is completely dissolved (-5 minutes)
- o The total volume of 40mg/ml reconstituted solution required should be calculated; equivalent volume should be removed from a 250ml bag of 0.9% sodium chloride
- o The total volume of 40mg/ml reconstituted solution should be withdrawn and slowly injected into the bag of 0.9% sodium chloride, producing a diluted tafasitamab concentration of 2mg/ml to 8mg/ml in a total volume of 250ml
- o Gently invert the bag (to not shake) to mix
- o Unused reconstituted solution should be discarded
- Handling and storage
 - o Unreconstituted vials should be protected from light, stored in refrigeration (2°C to 8°C; 36°F to 46°F), and must not be frozen
 - o Reconstituted solution should be protected from light and used immediately; if not used immediately:
 - Do not freeze
 - Store in refrigeration (2°C to 8°C; 36°F to 46°F) for up to 18 hours, or
 - Store at room temperature (20°C to 25°C; 68°F to 77°F) for up to 12 hours, inclusive of time for infusion
- Source of Supply: investigational supply of tafasitamab will be supplied by Morphosys

5.2 Lenalidomide

Lenalidomide is an orally-administered IMiD manufactured by Celgene. Generic formulations of lenalidomide were approved by FDA in May 2021 and are anticipated to become available in March 2022. Information below is for lenalidomide manufactured under brand name by Celgene; details of generic manufacturers' formulations are not yet available. Lenalidomide will be obtained commercially based on an approved FDA indication in MCL.

- Dose formulation: Lenalidomide is available as capsules ranging in strength from 2.5mg to 25mg
 - o 2.5mg (bottles of 28 or 100): white and blue-green opaque hard capsules, imprinted "REV" on one half and "2.5 mg" on the other half in black ink
 - o 5mg (bottles of 28 or 100): white opaque capsules imprinted "REV" on one half and "5 mg" on the other half in black ink
 - o 10mg (bottles of 28 or 100): blue/green and pale yellow opaque capsules imprinted "REV" on one half and "10 mg" on the other half in black ink
 - o 15mg (bottles of 21 or 100): powder blue and white opaque capsules imprinted "REV" on one half and "15 mg" on the other half in black ink
 - o 20mg (bottles of 21 or 100): powder blue and blue-green opaque hard capsules imprinted "REV" on one half and "20 mg" on the other half in black ink

- 25mg (bottles of 21 or 100): white opaque capsules imprinted "REV" on one half and "25 mg" on the other half in black ink
- Packaging and labeling of lenalidomide will be determined by the external commercial specialty pharmacy filling the prescription, in accordance with governing regulatory agencies
- Handling and storage:
 - Lenalidomide should be stored at room temperature (20°C to 25°C; 68°F to 77°F) in the original packaging dispensed to the patient; excursions to 15°C to 30°C (59°F to 86°F) are permissible
 - Care should be taken in handling lenalidomide; capsules should never be opened or broken
 - If a patient's skin comes into contact with powder from a lenalidomide capsule, the skin should be immediately and thoroughly washed with soap and water; if a patient's mucous membranes come into contact with powder from a lenalidomide capsule, immediately and thoroughly flush with water
- Source of supply:
 - Commercial supply of lenalidomide (branded or generic product as available and accessible for the patient) will be prescribed by the investigator to a commercial specialty pharmacy according to patient's and/or patient's prescription drug insurance's preference
 - For patients without prescription drug insurance, whose prescription drug insurance does not cover lenalidomide, or whose copay for lenalidomide is financially burdensome, enrollment in the BMS Access Support program will be sought prior to study initiation (see Section 9.0 Pre-Treatment)

6.0 CRITERIA FOR PARTICIPANT ELIGIBILITY

Patients will be relapsed or refractory MCL patients who have previously failed or did not tolerate BTKi therapy.

6.1 Participant Inclusion Criteria

Patients must meet all of the following criteria to be eligible for inclusion in this study:

- Age ≥ 18 years at the time of signing Informed Consent
- Karnofsky performance status (KPS) ≥ 70% (see Appendix A)
- Pathologically confirmed diagnosis of R/R MCL
- Previously treated with at least one prior line of systemic therapy for MCL, at least one of which must have been a BTKi
- If patient previously received CD19-directed therapy (such as CAR-T therapy), then there must be evidence of CD19 expression confirmed by immunohistochemistry or flow cytometry per institutional guidelines. This must be confirmed on a biopsy performed after receipt of CD19-directed therapy.

- Previous systemic chemotherapy must have been discontinued at least 2 weeks prior to C1D1 and previous anti-cancer radiation therapy or targeted therapy must be discontinued prior to initiation of treatment on study
 - All adverse effects should resolve to grade 1 or baseline (excluding alopecia)
- Presence of evaluable disease
- Adequate bone marrow and organ function:
 - Absolute neutrophil count (ANC) 2: 1,500 cells/mcL, unless felt to be secondary to underlying MCL
 - Platelet count 2: 90,000 cells/mcL, unless felt to be secondary to underlying MCL
 - Renal function assessed by calculated Cockcroft-Gault creatinine clearance (CrCl; see Appendix B) 2: 30ml/min. See 10.0 Treatment Plan, Table 10-1, for lenalidomide dose adjustment for CrCl 2: 30ml/min and < 60ml/min.
 - Hepatic function:
 - Total bilirubin < 2.5x upper limit of normal (ULN), unless secondary to Gilbert's syndrome or documented liver involvement by lymphoma. Patients with Gilbert's syndrome or documented liver involvement by lymphoma may be included if total bilirubin is ≤ 5x ULN.
 - Aspartate transaminase (AST) and alanine transaminase (ALT) ≤ 3x ULN, unless secondary to documented liver involvement by lymphoma. Patients with documented liver involvement by lymphoma may be included if AST and ALT are ≤ 5x ULN.
- Willingness to receive adequate prophylaxis and/or therapy for thromboembolic events, unless contraindicated in the opinion of the investigator
- Willingness to undergo confirmatory procedures for assessment of disease status and experimental studies as required by protocol, including bone marrow (BM) aspiration/biopsy, gastrointestinal endoscopy/colonoscopy with biopsy, and/or biopsy of other tissue when appropriate and medically feasible
- Each patient must sign Informed Consent form indicating that he or she understands the purpose of and procedures required for the study and are willing to participate
- Short course systemic corticosteroids (total daily dose equivalent of prednisone 100mg or less) are permissible for disease control, improvement of performance status, or non-cancer indication if administered for ≤ 10 days and discontinued prior to initiation of study treatment
- Willingness of patients who are able to become pregnant according to Revlimid/lenalidomide Risk Evaluation and Mitigation Strategy (REMS) criteria to undergo pregnancy testing in accordance with REMS requirements
- Willingness of all patients to adhere to contraception requirements mandated by the Revlimid/lenalidomide REMS

